## Opioid use in CVS and the critical need for opioid sparing therapy

Given the lack of knowledge about pathophysiology and evidence-based therapies, patients are often hospitalized to treat symptoms of CVS. During an episode, patients present with severe vomiting and abdominal pain and are treated empirically with IV fluids, antiemetics, benzodiazepines, and opioids. Estimates of opioid use range from 23%-27% in adults with CVS. Patients are often dissatisfied with the level of analgesia as recurrent opioid use results in tolerance and dependence. This often undermines the physician-patient relationship and patients even leave against medical advice out of frustration with what they perceive as ineffective care. This can lead to worse outcomes including recurrent hospitalizations, morbidity and increased health care costs.

Preliminary data from a study by our group reveals that of 101 patients hospitalized with CVS at Froedtert Hospital, chronic opioid therapy is associated with a two-fold increased risk of hospitalization (RR 2.22, CI 1.1-4.4, P=0.02) and three-fold increase in hospital length of stay (LOS) (RR 3.43, CI 1.26-9.34, P=0.01). In a study of 132 CVS patients, opioid use was associated with non-response to amitriptyline (53% vs 15%, p<0.05), a prophylactic therapy used in CVS. In turn was associated with increased frequency and duration of CVS episodes per year and increased number of hospitalizations/emergency

department (ED) visits at baseline (18% vs 15.2%, p<0.05). Hence there is an urgent need for an opioid-sparing, non-invasive strategy to treat CVS symptoms.

In summary, CVS is common and disabling and is associated with significant health care costs. Much of this burden can be tied to iatrogenic opioid overuse, resulting in chronic opioid use and high risk of addiction and health care utilization. Understanding the pathophysiology of CVS and development of novel therapies are urgently needed. Further, similar to other disorders with rampant opioid use, **there is a critical need for opioid-sparing therapy in CVS to negate the devastating short and long-term effects of opioid use**. Our proposed project using a novel, non-invasive device to treat CVS will also address the current opioid crisis.

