## (C) Approach, Feasibility, and Environment

## Aim 1: Investigate the efficacy of PENFS in adults admitted with cyclic vomiting syndrome

## Methods

**Inclusion/Exclusion Criteria.** We will enroll 80 adults between the ages of 18-65 years with a diagnosis of CVS (based on Rome IV diagnostic criteria). This study will only include patients who are admitted to Froedtert Hospital with an episode of CVS. Exclusion

criteria includes developmental delays, non-English speaking patients, pregnancy, any implanted electrical device or any significant dermatological/infectious condition of the ear.

Randomization. Subjects will be randomized to the intervention group (receiving the Bridge device) or control group (receiving an identical sham device lacking electrical charge) in 1:1 ratio. The auricular neurostimulator device will be placed on the subject's ear upon presentation to the hospital. The device delivers low voltage (3.2), continuous stimulation for 5 days (around the clock) in alternating frequencies (1-10Hz) with an impulse interval of 100ms/2 sec. The neurostimulators (for both treatment arms) will be placed by a certified MD/APP/RN inside the patient's room. All patients will be allowed to receive rescue medications after implantation of the device if the symptoms do not improve with the device or at patient's request.

We have performed a sample size calculation based on prior data. At a significance level of 0.05 and 80% power, we estimate a sample size of 40 participants per group to detect the minimum standardized effect size of 0.64 using two-sided tests, using prior data. We will compare the different variables (average daily reduction in abdominal pain, nausea/vomiting scores, average daily use/frequency/dosage of rescue medications (opiates, antiemetics and sedatives between PENFS vs sham device.

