Outcomes. Primary outcome will include the change in abdominal pain and concurrent opioid use. Abdominal pain will be assessed daily through Visual Analog Scale with the score ranging from 0 to 10, with 0 being the least and 10 being the worst pain. The need for opiates will be assessed through- (a) the time taken by the subject from the time of admission to the first felt need accompanied by the actual administration of opiates (IV hydromorphone or morphine), (b) daily frequency and total dosage of opiates received. Secondary outcomes will include- (a) severity of daily nausea and vomiting assessed through the Index for Nausea, Vomiting and Retching (INVR); (b) the need for other rescue medications (which include antiemetics like ondansetron, promethazine & metoclopramide; benzodiazepines like lorazepam; antihistaminics like diphenhydramine, etc.), (c) hospital LOS and (d) survey on patient satisfaction. While all other outcomes will be assessed daily, LOS and patient satisfaction will be assessed at the time of discharge (Table 1). All variables will be compared between the subjects in intervention arm versus control arm.

We hypothesize that PENFS will effectively mitigate the abdominal pain, nausea and vomiting associated with CVS episodes, obviate or reduce the need for opiates and simultaneously improve healthcare outcomes including LOS and patient satisfaction.

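### Chronic opioid use, which the plan's own data associate with length of stay, is not used in allocation or analysis; stratifying and adjusting on it would be a cheap gain in precision

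*Combined protocol and SAP*

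**What the plan says.** Under (C) Approach, Feasibility, and Environment, the Methods section states the size of the trial: "We will enroll 80 adults between the ages of 18-65 years". On allocation it gives the two arms and the ratio, the second arm being the "control group (receiving an identical sham device lacking electrical charge) in 1:1 ratio". It mentions no sequence method, blocking, stratification or minimisation. The exclusion list has no opioid-related item, so chronic users can enter.

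On analysis, the outcomes paragraph says "All variables will be compared between the subjects in intervention arm versus control arm". The Statistical Analysis paragraph adds summary statistics, transformation or non-parametric tests, and Chi-square or Fisher's exact tests for binary outcomes. No regression, ANCOVA or baseline covariate is named. Table 1 schedules pain, INVR and the need for opiates at admission, but has no entry for opioid use before admission.

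The section on opioid use in CVS reports preliminary data from 101 patients hospitalized at the trial's own hospital: "chronic opioid therapy is associated with a two-fold increased risk of hospitalization (RR 2.22, CI 1.1-4.4, P=0.02") and a "three-fold increase in hospital length of stay (LOS) (RR 3.43, CI 1.26-9.34, P=0.01"). It also says "Estimates of opioid use range from 23%-27% in adults with CVS".

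Length of stay is a secondary outcome. Opioid use (time to first opiate, daily frequency and total dosage) is part of the primary outcome, together with change in pain.

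**The concern.** The plan identifies a baseline factor associated with one of its outcomes, at the same hospital, and then makes no stated use of it. With 40 patients per arm, unstratified allocation can leave a factor carried by about a quarter of patients unequal between arms. If that factor is as prognostic as the preliminary data suggest, two things follow for length of stay. The observed difference in a given trial can be moved up or down by the imbalance alone. And the variance due to the factor stays in the error term, so a real effect is harder to detect. The same may apply to the opioid-use part of the primary outcome, since prior chronic use plausibly affects in-hospital opioid need. The documents give no figure for that link.

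**Working it through.** **The plan's own figure.** The Methods section gives these inputs: "At a significance level of 0.05 and 80% power, we estimate a sample size of 40 participants per group". The target difference there is 0.64 SD, tested two-sided. By the normal approximation, n per arm = 2 × (1.960 + 0.842)² / 0.64² = 38.3, so 39. The two-sample t-test gives 39.3, so 40. Power at 40 per arm is 0.807. The stated size reproduces as an ordinary two-group comparison without covariates.

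**Chance imbalance.** Assume 23-27% are chronic users. The documents give this range for opioid use in adults with CVS, so it is a proxy. Take the number of users in each arm as Binomial(40, p). The SD of the between-arm difference is √(2p(1−p)/40), or 9.4 to 9.9 percentage points. Exact probabilities:

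| Gap between arms | p = 0.23 | p = 0.25 | p = 0.27 |
|---|---|---|---|
| ≥ 10 points (4 of 40) | 0.351 | 0.365 | 0.377 |
| ≥ 15 points (6 of 40) | 0.143 | 0.155 | 0.165 |
| ≥ 20 points (8 of 40) | 0.046 | 0.052 | 0.058 |

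**Effect of a 10-point gap on mean length of stay.** Assume the RR is a ratio of means, with 30% users in one arm, 20% in the other, and identical treatments. The ratio of arm means is (1 + (RR − 1) × 0.30) / (1 + (RR − 1) × 0.20).
- RR 3.43: 1.729 / 1.486 = 1.16
- RR 1.26 (lower limit): 1.078 / 1.052 = 1.025
- RR 9.34 (upper limit): 3.502 / 2.668 = 1.31

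**Power with and without the covariate.** Assume a true 30% reduction in length of stay (ln 0.70 = −0.357 on the log scale), 25% users and 40 per arm. The SD of log length of stay within user groups, s, is not in the documents and is varied. The unadjusted SD is √(s² + p(1−p)(ln RR)²). At RR 3.43 the added term is 0.25 × 0.75 × 1.233² = 0.285. Adjustment leaves s as the residual SD. Formula and simulation agree to within about a percentage point; approximate values are:

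| s | Unadjusted SD at RR 3.43 | Power unadjusted | Power adjusted |
|---|---|---|---|
| 0.6 | √(0.36 + 0.285) = 0.80 | 50% | 74% |
| 0.8 | √(0.64 + 0.285) = 0.96 | 38% | 51% |
| 1.0 | √(1.00 + 0.285) = 1.13 | 28% | 35% |

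At RR 2.0 and s = 0.6, power goes from about 66% to 75%. At RR 1.26 the added term is 0.010 and the gain is at most about one point.

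**The case against.** The strongest reply is that the plan is silent here, and silence is not a choice. A reader might infer that the sponsor opted for simple randomization and ruled out adjustment. The text says neither: it gives a ratio and arm-versus-arm comparisons, and names unadjusted tests only for binary outcomes. That stands. What remains is that the factor is not used anywhere in the stated plan, and Table 1 does not provide for collecting it.

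A reader might also infer that chronic opioid use makes stays three times as long, or is the strongest predictor of stay. The documents support neither. The figure is an association in 101 patients with a wide interval, it is not said whether it is a ratio of mean stays or a risk ratio for a long stay, and predictors are not ranked. If it is a risk ratio for a long stay, the 16% shift and the power figures do not follow from it.

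Nor is the trial invalid. Over all randomizations the unadjusted test keeps its 5% error, because chance imbalance is already part of its standard error. On the assumptions most favourable to the concern (RR 3.43, s = 0.6), a 10-point gap moves log length of stay by 0.10 × 1.233 = 0.123. The standard error is 0.80 × √(2/40) = 0.18, so the shift is about 0.7 standard errors.

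Finally, length of stay is secondary, and no figure in the documents links chronic use to pain, opioid dose or time to first opiate. This also stands, and it limits what can be claimed for the primary outcome.

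**Conclusion.** The point holds as a low-cost improvement in precision and does not amount to an error. The sample size of 40 per arm is correct for what it states, and overall type I error is preserved. What is lost is power for length of stay, and protection of the estimate in a trial that happens to be imbalanced on a factor the plan itself highlights.

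The size depends on three assumptions that the documents do not settle: that 23-27% approximates chronic use among these inpatients, that the RR acts as a ratio of mean stays, and the spread of log length of stay. At the reported RR the power gain runs from about 24 points (s = 0.6) to about 7 (s = 1.0). At the lower confidence limit it disappears. A benefit for the opioid-use part of the primary outcome is plausible but unquantified, and none can be claimed for pain.

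**What to change.** 1. Define chronic opioid use before admission as a yes/no item, and record it before randomization. Add it to the admission column of Table 1.
2. Randomize 1:1 in permuted blocks stratified by that item. With blocks of four, for example, the number of users can differ by at most two between arms, or about 5 points (2/40).
3. Prespecify the item as a covariate in the analyses of opioid dose, time to first opiate and length of stay. Where a non-parametric test is used instead, use its version stratified by the same item.

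The cost is one agreed definition, one chart item that must be available at screening before the device is placed, a two-stratum list and one model term. No extra patients or visits are needed. It should be settled before enrolment: allocation cannot be rebalanced afterwards, and a covariate added once data are seen would look data-driven.

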#### B) Innovation, Novel Technology and/or Novel Approach

#### **PENFS: a novel technology for the treatment of CVS**

The Bridge device (PENFS) is a novel technology that is designed to treat pain and also improves other symptoms such as nausea and vomiting. The Bridge device has recently been approved by the FDA for treating opioid withdrawal symptoms including pain, nausea, vomiting, insomnia and agitation. Most recently, it has also been shown to be a safe and effective therapeutic option for adolescents with abdominal pain-related functional gastrointestinal disorders, resulting in reduction in abdominal pain and global symptom imrovement. *If our study shows the efficacy of the Bridge device compared to sham in mitigating pain, nausea and vomiting, it will have the potential to transform the clinical care of CVS patients with the advent of an innovative, opiate sparing, non-invasive technology.* Further, our purposed device through its effectiveness in resolution of symptoms will improve *patient satisfaction*, reduce hospital LOS and overall health care costs. *More importantly, it will address the current opioid crisis that affects patients with CVS and potentially can be applied to other chronic disorders associated with pain.* 

In summary, our study attempts to **shift the current clinical practice paradigm** in CVS and enhance our understanding of the pathophysiology through the use of PENFS device as a novel, non-invasive **approach in mitigating the detrimental effects from opioids** in CVS. Additionally, this device can also be used in the treatment of other chronic pain disorders.

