**Table 1. Study Protocol** 

Tubic 1. Study	1100001					
	Admission (0 hours)	2 hours post - placement	24 hrs.	Daily	5 days*	Discharge
Screening & Consent	X					

Demographics	X					
Neurostimulator (PENFS) vs sham	X	X	X	X	X	
Rome IV questionnaire 	X					
INVR (vomiting scale; daily during therapy) 	X	X	X	X	X	X
Abdominal pain (Visual Analogue Scale)	X	X	X	X	X	X
Need for opiates and other rescue medications	X	X	X	X	X	X
Length of stay						X
Patient Satisfaction Survey						X

INVR=Rhodes Index of Nausea, Vomiting & Retching; CGRP= Calcitonin Gene-Related Peptide

**Statistical Analysis:** Summary statistics, such as mean, median, standard deviation and range will be used as a first step to examine data. To satisfy parametric assumptions, we may perform transformations with justifications if possible and otherwise use non-parametric tests. For any binary outcomes, we will use Chi-square or Fisher's exact tests to compare the proportions between the two groups. We will compare the different variables (average daily reduction in abdominal pain, nausea/vomiting scores, average daily use/frequency/dosage of rescue medications (opiates, antiemetics and sedatives) between PENFS vs sham device. Data analyses will be performed using SAS version 9.4 (SAS institute, Cary, NC).

**Potential Pitfalls:** This pilot data is both safe and non-invasive and will help us better understand the pathophysiology underlying CVS symptoms. The proposed device is non-invasive and currently utilized at our institution. The PI is certified in the PENFS placement and has already used it in some of her patients with success. We thus expect no feasibility or safety issues. Potential risks generally would include bleeding or infection at the puncture site, pain at the application site, or skin irritation at the site of application.

**Feasibility**: Recruitment should not pose a problem as the PI ([name]) has the largest cohort of patients with CVS in the nation. Further in our experience, CVS sufferers are also highly motivated to enroll in studies and trial new therapies The PI also works closely with the Cyclic Vomiting Syndrome Association, who will advertise the study on their website and

\* questionnaires will be completed as an outpatient if patient is already discharged

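### Pain change and three opioid measures are all primary with no rule for success, so the stated 5% significance level and 80% power do not describe the trial's overall conclusion

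*Combined protocol and SAP*

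**What the plan says.** The Outcomes paragraph in section (C) states "Primary outcome will include the change in abdominal pain and concurrent opioid use". Before it turns to secondary outcomes, it says how opioid need is assessed: (a) "the time taken by the subject from the time of admission to the first felt need accompanied by the actual administration of opiates", and (b) "daily frequency and total dosage of opiates received". Item (a) is one measure and item (b) names two, so with pain there are four primary measures. The paragraph ends "All variables will be compared between the subjects in intervention arm versus control arm".

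The sample-size text, also in section (C), gives one calculation: significance level 0.05, 80% power and 40 per group "to detect the minimum standardized effect size of 0.64 using two-sided tests". It cites prior data but does not say which endpoint the 0.64 belongs to.

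The Statistical Analysis paragraph lists what will be compared, starting with "average daily reduction in abdominal pain, nausea/vomiting scores" and going on to rescue-medication use. It covers summary statistics, transformations or non-parametric tests, and chi-square or Fisher tests. Nowhere is there a composite, a co-primary rule, an order of testing, a split of alpha or a success criterion.

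Table 1 marks the need for opiates in the 5-day column. That column's footnote says "questionnaires will be completed as an outpatient if patient is already discharged".

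**The concern.** Four primary measures tested without a rule leave the trial's conclusion open. The same data could be reported as positive or not, depending on which measure is put forward.

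This matters more than usual here because the two domains can trade off. Rescue medication may be given at the patient's request, so lower pain could come with more opioid, and lower opioid use with more pain. Neither result can be interpreted without the other.

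The plan also attaches a formal significance level and power to an efficacy aim against sham. Readers will take 5% and 80% as properties of the trial's conclusion, but they are properties of one comparison.

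**Working it through.** **1. The plan's own figure.** Inputs from the sample-size text: d = 0.64, two-sided alpha 0.05, 40 per group, 1:1. For a two-sample t-test the noncentrality is d·√(n/2) = 0.64 × √20 = 2.862 on 78 degrees of freedom. Power is 80.7% at 40 per group and 79.7% at 39. The stated 40 is therefore correct for one comparison of means at the full 0.05. (The normal approximation gives 81.7% at 40.)

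**2. Assumptions for what follows.** The documents give no correlation between measures and no effect size for opioid use. I use approximately normal test statistics, correlations of 0.2-0.5 between pain and opioid use, and two ranges among the opioid measures: 0.8-0.9 and 0.3-0.6.

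**3. Reading (a): any of the four counts, each at 0.05.**
- Independent: 1 − 0.95⁴ = 18.5%. This is an upper reference value.
- Opioid measures correlated 0.8: 14.1%, 13.8% and 13.3% for pain-opioid correlations of 0.2, 0.35 and 0.5.
- Opioid measures correlated 0.9: 12.8%, 12.5% and 12.0%.
- Opioid measures correlated 0.3-0.6: about 15-18%.
- All four correlated 0.9 with each other: 9.4%, still above 5%.
- Counting only false wins for the device, the 0.8-0.9 range gives about 6-7%, against 2.5% for one test.

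**4. Reading (b): pain and one opioid measure fixed in advance must both succeed.** A false claim requires a false positive on at least one named test, so error is at most 5%. Power with d = 0.64 on both:
- Independent: 0.807² = 65.1%.
- Simulated t-tests, correlations 0, 0.5 and 0.8: 65.1%, 69.7% and 73.7%.
- If one of the effects is 0.4 instead, 34-42%.
- A common effect of about 0.68-0.72 is needed for 80%.

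**5. Reading (c): pain and any one of the three opioid measures.** Suppose pain truly improves and opioid use does not change. With opioid correlations of 0.8-0.9, a false joint claim occurs in about 6-8% of trials at a pain effect of 0.64, and in about 8-10% at 1.0, where pain is almost always significant. In the device's favour it is about 4-5%, against 2.5%. Power with 0.64 on all measures is about 73-77%.

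**6. Reading (d): all four must succeed.** Power is about 60-66% at the same correlations. The power figures in (c) and (d) use the normal approximation and so are slightly generous.

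**7. Power under the remedy.** One endpoint at alpha 0.025, Holm's first step: 71.7%. Both endpoints significant under Holm (smaller p-value at most 0.025, larger at most 0.05): 64.3%, 68.6% and 72.1% at correlations 0, 0.5 and 0.8.

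**The case against.** **The outcome may be a joint one.** The singular wording and the word concurrent allow a both-must-succeed reading, under which no alpha adjustment is needed. That is fair, and it rules out saying that error is inflated on every reading. But the protection holds only if one opioid measure is fixed in advance, and three are listed with none chosen. Power then falls below 80% at the plan's own effect size.

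**The calculation may cover every comparison.** The sample-size text speaks of tests in the plural and of a minimum effect, then lists the variables to be compared. A reader might infer that the trial was sized for one specific endpoint. The text does not establish that, since 0.64 may be meant as the detectable effect for each variable. Even so, it gives per-test power only, with no overall error rate or power.

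**The narrative sections may settle the matter.** A reader might infer from Special Emphasis, which makes replacing intravenous opiates the main focus, that opioid use decides. The Innovation section instead conditions success on pain, nausea and vomiting, and presents change in care "with the advent of an innovative, opiate sparing, non-invasive technology" as what would follow. The two differ in emphasis, and neither names a deciding endpoint.

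**It is a pilot.** The Potential Pitfalls and Future Plans text describe pilot or preliminary data meant to support a larger trial. This lowers the stakes but does not supply the missing rule.

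**The magnitudes rest on assumed correlations.** This stands. Time to first opiate is a different kind of variable from total dose, so high correlations among the opioid measures cannot be taken for granted. That is why ranges are given.

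**Conclusion.** The concern holds. Four measures are primary, no rule says which results make the trial positive, and the effect size is tied to no endpoint. The sample-size arithmetic itself is sound.

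None of the four readings delivers both 5% error and 80% power at an effect of 0.64. Reading (a) loses error control; (b) and (d) lose power; (c) loses some of each. The absence of a rule is certain from the text. The sizes depend on assumed correlations, approximate normality and an effect of 0.64 on opioid use that the documents do not support.

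A reader might quote 18.5% as the error rate of this trial. That figure needs independent measures, which is implausible for three measures of the same opioid use, so it is only an upper reference.

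The sponsor should correct this. The pilot purpose keeps it short of a fatal flaw.

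**What to change.** Before any comparison by arm:

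1. Name two primary endpoints: the average daily reduction in abdominal pain already listed in the analysis text, and one opioid measure. Total dose in one common unit is a reasonable choice, but this is a judgement and the sponsor may prefer another. Make the other opioid measures secondary. The Significance section puts opioid use at 23-27% in adults with CVS, although inpatient use may be higher. If many patients receive no opiates, use a method suited to many zeros.
2. Claim opioid-sparing pain relief only if both endpoints are significant in favour of the device, each at two-sided 0.05.
3. If a claim on one endpoint alone is also wanted, use Holm at family-wise 0.05 and report the other endpoint's estimate and confidence interval beside it. One named primary, or a fixed sequence, is an acceptable alternative that keeps about 80% power for the first test.
4. State which endpoint 0.64 refers to. Restate power at 40 per group: about 80% for one test at 0.05, 72% for one endpoint at 0.025, and 65-74% for the joint claim at 0.05 each (64-72% under Holm). Label the figures as assuming 0.64 on both endpoints, correlation 0 to 0.8 and approximately normal data.
5. Say how opioid use between discharge and day 5 is counted. Table 1 marks opiate need at 5 days, but the footnote refers only to questionnaires, and it is unclear whether that covers the opiate row.

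**Cost.** No extra patients. The outcome and analysis text must be revised, and a stated opioid conversion is needed if total dose is chosen. Two opioid measures become supportive, and the stated power is less favourable than 80%.

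### Time to first opioid, part of the primary outcome, has no value for patients who never receive one, and the plan names no rule or censored-data method for them

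*Combined protocol and SAP*

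**What the plan says.** The Outcomes paragraph (section C, Methods) puts opioid use in the primary outcome beside change in abdominal pain. Need for opiates is measured in two ways. The first is "the time taken by the subject from the time of admission to the first felt need accompanied by the actual administration of opiates", with the opiates specified as IV hydromorphone or morphine. The second is "daily frequency and total dosage of opiates received". The paragraph ends its list with "All variables will be compared between the subjects in intervention arm versus control arm". The hypothesis that follows is that the device will "obviate or reduce the need for opiates and simultaneously improve healthcare outcomes including LOS and patient satisfaction".

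The Statistical Analysis paragraph, after Table 1, says of parametric assumptions that "we may perform transformations with justifications if possible and otherwise use non-parametric tests". It continues "For any binary outcomes, we will use Chi-square or" Fisher's exact tests. The variables it lists for comparison include "average daily use/frequency/dosage of rescue medications (opiates, antiemetics and sedatives) between PENFS vs sham device". Time to first opioid is not in that list, nor in the similar list in the Randomization paragraph, so only the general sentence in Outcomes covers it.

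On timing, the Randomization paragraph has the device placed when the patient presents and allows rescue medication after that. Table 1 marks consent, device and opioid need all in the hour-0 admission column, and times the next column from placement. No maximum delay from admission to placement is given. A Table 1 footnote to the 5-day column has questionnaires completed as an outpatient after early discharge.

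**The concern.** The measure is a time that exists only for patients who receive an opioid. Patients who get through the episode without one have the best possible result and no number. The plan does not say whether they are ranked last, treated as censored or left out, so that choice could be made after the data are seen, and different choices can give different answers. The worst choice is also the easiest to make by default: software given a column of observed times will silently omit the blanks. The comparison is then between opioid users in each arm, a subgroup formed after randomization and shaped by the treatment itself.

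The secondary question is the starting point. Treatment cannot act before it is applied, yet the clock runs from admission. A dose given between admission and randomization or placement would be scored as an outcome event.

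**Working it through.** **The plan's own figure.** For a standardized effect of 0.64, two-sided 0.05 and 80% power, n per group = 2(1.96 + 0.84)²/0.64² = 38.3, so 39. The t-test solution is 39.3, so 40. The stated 40 per group reproduces. It is a comparison of two means and says nothing about a time-to-event measure.

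**Inputs.** From the documents: 40 per arm, two-sided 0.05, and a 5-day device period (5 × 24 = 120 h). Assumed: a hazard ratio of 0.5, a constant hazard, and sham opioid use within 120 h of u = 27, 50, 75 or 90%. The documents give no inpatient rate. The background section reports 23–27% for adults with CVS generally, and section D says only that admitted patients often need IV opioids.

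**Patients with no value.** Expected number = 40(1 − u) + 40(1 − u)^0.5.
- u = 0.27: 29.2 + 34.2 = 63.4 of 80
- u = 0.50: 20.0 + 28.3 = 48.3
- u = 0.75: 10.0 + 20.0 = 30.0
- u = 0.90: 4.0 + 12.6 = 16.6

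**Power by handling** (simulation, 4,000 runs; repeat runs agreed within simulation error):

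| Analysis | u = 27% | 50% | 75% | 90% |
|---|---|---|---|---|
| Log-rank, all patients | 28% | 49% | 68% | 79% |
| Mann-Whitney, never-users ranked last | 28% | 47% | 65% | 71% |
| Fisher, any opioid use | 21% | 39% | 55% | 59% |
| Mann-Whitney, users only | 4% | 5% | 10% | 20% |
| t-test on log time, users only | 4% | 5% | 9% | 17% |

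Ranking never-users last costs 0, 2, 3 and 8 points against the log-rank. Leaving them out costs 24, 44, 58 and 59 points.

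The loss arises because most of the effect lies in who needs an opioid at all. In a companion run at u = 50%, an average of 11.7 device patients and 19.9 sham patients of 40 received one, but the mean time among users was 2.34 against 2.22 days. With no true effect, the users-only t-test in that run rejected about 5% of the time. In this simple model the harm is therefore a missed effect, not a false positive.

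**Clock.** The documents give neither the delay from admission to placement nor any count of opioids given in it, so the size cannot be computed. An illustration with invented rates shows what it depends on. Take u = 75% and let 10/20/30% of patients receive an opioid before randomization.
- Admission clock: power about 58/45/34%, against 69% with no such doses.
- Randomization clock, stratified log-rank, device fully effective in those patients afterwards: about 70/66/67%.
- Randomization clock, but those patients re-dosed soon regardless of arm (mean 4 h): about 58/47/35%, hardly better than the admission clock.

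**The case against.** The strongest reply is that the plan never says never-users are dropped. It promises non-parametric tests without naming any for non-binary outcomes. The log-rank is non-parametric, and so is a rank test with never-users last. On the figures above, a sensible statistician working within the present text would lose at most about 8 points. Daily frequency and total dosage score a never-user as zero, and those are the opioid measures the analysis section actually lists. The study also describes itself as a pilot.

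Most of this stands. A reader might infer that the plan excludes opioid-free patients, or that its methods cannot accommodate them. The documents support neither reading. What remains is that no rule is stated and no suitable test is named for a measure within the primary outcome. The one very costly choice is also not ruled out.

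On the clock, a reader might infer that every opioid given before treatment counts as an event. It does not: a dose before admission falls before time zero, and the definition is limited to IV hydromorphone or morphine. Only the interval from admission to randomization or placement is in question, and the plan means it to be short. Nor is it a bias between arms. Randomization makes such doses equally likely in both, so the effect is dilution. Moving the clock cannot be promised to restore power either, as the last illustration shows.

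**Conclusion.** The point holds and should be fixed. Time to first opioid is undefined for patients who never receive one, and the plan gives neither a rule for them nor a named censored-data method. The consequence depends on a choice the plan leaves open: about 0 to 8 points of power if never-users are ranked last, and most of the power if only users are compared. These figures rest on an assumed hazard ratio of 0.5, a constant hazard and assumed sham use of 27–90%. The gap in the definition rests on the text alone. It does not touch the frequency and dosage measures and does not invalidate the trial.

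The admission clock is a lesser point. By definition it can count events that treatment could not affect, but the dilution is of unknown and possibly zero size. The benefit of correcting it depends on whether the device still affects later dosing in those patients.

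**What to change.** - Define the measure as time from randomization to first in-hospital administration of the opiates already named in Outcomes, and say whether felt need remains part of the event.
- Keep all randomized patients. Compare arms by Kaplan-Meier curves and one named log-rank test to 120 h.
- Record any opioid given before randomization as a baseline variable, not an event, and stratify the test by it if it occurs.
- Record the times of randomization and placement. Use placement, which happens in both arms, as time zero in a sensitivity analysis, because doses between the two still count in the main one.
- State in advance how discharge without an opioid is handled (for example, event-free to 120 h or censored at discharge), with the alternative rule as a sensitivity analysis. Say whether the Table 1 outpatient footnote covers opioid need after discharge.
- Reconcile the admission, presentation and placement wording across the Randomization paragraph, Outcomes and Table 1.

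The cost is a few lines of text, two recorded times and slightly more analysis. No extra patients or visits are needed.
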